7.6.6 Other Analysis of Secondary Efficacy Endpoints

The analysis of efficacy of the above-mentioned endpoints (primary endpoint and secondary endpoints included in the hierarchical analysis) will be conducted at timepoints other than Week 6 in the DBPC Cycle and is described below (except urodynamic endpoints as only performed at Week 6). The analysis of other secondary endpoints (see Section 3.2) is also described below.

Descriptive summaries will be performed for the DBPC Cycle and by Dysport Cycles (i.e. Dysport Cycle 1, Dysport cycle 2 ...), see the schematic diagram in Section 7.1.

Statistical comparison analyses are only applicable for the DBPC treatment cycle. Analyses between treatment groups, Dysport 600 U vs. Placebo, and Dysport 800 U vs. Placebo will be performed accordingly using GLMM and MMRM as mentioned below for each endpoint. As all subjects should have visits up to and including week 12, but thereafter visits are dependent on whether the subject receives retreatment, statistical testing between treatment groups will be

performed only up to Week 12, inclusive. All secondary endpoints not included in the hierarchical analysis are considered as exploratory endpoints and will therefore be analysed for exploratory purposes only to compare each Dysport dose to placebo, alpha at 0.05 level.

7.6.6.1 Diary Parameters

Refer to Section 3.2 for details of diary parameter endpoints.

7.6.6.1.1 Weekly Number of UI Episodes

Mean change from study baseline

For both the DBPC Cycle and the Dysport Cycles, summary tables for mean values in each assessment visit and the mean change from study baseline will be presented using descriptive statistics

For the DBPC treatment cycle, mean change from study baseline to Week 2, and Week 12, will also be analysed using MMRM, using data from Week 2, 6 and 12, as in the primary efficacy analysis in section 7.6.3.

Thresholds of reduction

For both the DBPC Cycle and the Dysport Cycles, the number and percentage of subjects with UI will be summarised by improvement levels from study baseline ($\geq 30\%$ improvement, $\geq 50\%$ improvement, $\geq 75\%$ improvement, 100% improvement (no episodes of UI)) for each assessment visit.

Bar charts will also be plotted. For the DBPC treatment cycle, the GLMM for repeated measures will be fitted for UI responses using repeated measurements at Week 2, Week 6, Week 12. Each UI response level compared to study baseline ($\geq 30\%$ improvement, $\geq 50\%$ improvement, $\geq 75\%$ improvement or 100%) will be analysed as a response variable in each model, as described for the proportion of subjects with no UI episodes in section 7.6.5.

7.6.6.1.2 Daily Urinary Frequency and Voided Volume

For both the DBPC Cycle and by Dysport Cycles, the summary tables for mean values in each assessment visit and the mean change from study baseline will be presented using descriptive statistics.

For the DBPC treatment cycle, mean change from study baseline to Week 2, Week 6, and Week 12 will be analysed using MMRM, as in the primary efficacy analysis presented in Section 7.6.4.2.

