6.4.1.1 Clean Intermittent Catheterisation

All subjects in this study have significant bladder dysfunction and voiding difficulty, requiring routine CIC usage to adequately and regularly drain urine from the bladder.

At Screening, subjects must be routinely performing CIC to manage their bladder function, and ensure regular and adequate bladder emptying. CCI [REDACTED]

[REDACTED]

[REDACTED]

[REDACTED]

[REDACTED]

[REDACTED]

The CIC regimen should be maintained throughout the study; CCI [REDACTED]

[REDACTED]

[REDACTED]

[REDACTED]

[REDACTED]

[REDACTED]

[REDACTED]

6.4.1.2 *Antibiotic Prophylaxis*

Antibiotic prophylaxis is required in the study to cover:

(a) All urodynamic procedures:

- CCI [REDACTED]

(b) All IMP cystoscopic treatment administration procedures:

- CCI [REDACTED]

The minimum duration of the antibiotics can be lengthened per clinical judgment of the investigator.

Antibiotics may be:

- Adapted:
 - based on a recent urine culture and sensitivity test from the subject to determine the most appropriate antibiotic.
- Empiric:
 - based on the best judgement of the investigator, using knowledge of the likely bacteria, the individual subject and local antibiotic resistance and sensitivity patterns.
 - the investigator should ensure that there is no potential risk of colonisation with resistant bacteria to the chosen antibiotic (e.g. multiple recent courses of the same class of antibiotic).

Permitted Antibiotics

All oral antibiotics (except aminoglycoside antibiotics) available locally for the treatment of UTIs may be used at the discretion of the investigator.

The investigator must ensure that the subject has no known history of contraindications (e.g. allergy) to any antibiotics that are dispensed during the study.

Appropriate Usage of Prophylactic Antibiotics

CCI [REDACTED]

[REDACTED]

[REDACTED]

Antibiotic Prophylaxis During Screening

CCI [REDACTED]
[REDACTED]
[REDACTED]
[REDACTED]

Antibiotic Prophylaxis During Follow-up

CCI [REDACTED] [REDACTED] [REDACTED] [REDACTED] [REDACTED] [REDACTED] [REDACTED] [REDACTED] [REDACTED] [REDACTED]
[REDACTED]
[REDACTED]
[REDACTED]
[REDACTED]

[REDACTED]
[REDACTED]

CCI

CCI [REDACTED]

[REDACTED]

CCI

6.4.1.3 *Antibiotics for Symptomatic UTI*

Subjects with NDO may demonstrate atypical symptoms for UTI. If there is any suspicion of a UTI then the subject should be immediately commenced on appropriate antibiotics:

- CCI [REDACTED]
[REDACTED]
 - | [REDACTED]
[REDACTED]
[REDACTED]

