24-hour voided volume on 1 day of 7-day bladder diary (spontaneous voiding only)	Study Baseline (Screening) or treatment cycle baseline Week 2 Week 6 Week 12 Every 12 weeks thereafter until retreatment EOS Visit.	24-hour voided volume (spontaneous voiding only)	Mean change from study baseline to each subsequent timepoint within the treatment cycle in 24- hour voided volume (spontaneous voiding only)
24-hour voided volume on 1 day of 7-day bladder diary (CIC only)	Study Baseline (Screening) or treatment cycle baseline Week 2 Week 6 Week 12 Every 12 weeks thereafter until retreatment EOS Visit.	24-hour voided volume (CIC only)	Mean change from study baseline to each subsequent timepoint within the treatment cycle in 24- hour voided volume (CIC only)

Measure	Planned timepoints (dependent on timing of retreatments)	Variable	Endpoint
Total volume per void (spontaneous and CIC) on 1 day of 7-day bladder diary	Study Baseline (Screening) or treatment cycle baseline Week 2 Week 6 Week 12 Every 12 weeks thereafter until retreatment EOS Visit.	Total volume per void	Mean change from study baseline to each subsequent timepoint within the treatment cycle in total volume per void
Volume per void (spontaneous voiding only) on 1 day of 7-day bladder diary	Study Baseline (Screening) or treatment cycle baseline Week 2 Week 6 Week 12 Every 12 weeks thereafter until retreatment EOS Visit.	Volume per void (spontaneous voiding only)	Mean change from study baseline to each subsequent timepoint within the treatment cycle in volume per void (spontaneous voiding only)
Volume per void (CIC only) on 1 day of 7-day bladder diary	Study Baseline (Screening) or treatment cycle baseline Week 2 Week 6 Week 12 Every 12 weeks thereafter until retreatment EOS Visit.	Volume per void (CIC only)	Mean change from study baseline to each subsequent timepoint within the treatment cycle in volume per void (CIC only)
MCC measured by urodynamic filling cystometry	Study Baseline (Screening), Week 6	MCC	Mean change from study Baseline to Week 6 in MCC
MDP during storage measured by urodynamic filling cystometry	Study Baseline (Screening), Week 6	MDP	Mean change from study Baseline to Week 6 in MDP
Vol@1 st IDC measured by urodynamic filling cystometry	Study Baseline (Screening), Week 6	Vol@1 st IDC	Mean change from study Baseline to Week 6 in Vol@1 st IDC

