3.2 Secondary Efficacy Endpoints

The secondary efficacy endpoints are divided into those that relate to parameters measured in the bladder diary, those measured by urodynamic filling cystometry and those that are quality of life measures. From these secondary measures, there are several that have been selected to be analysed as part of a hierarchical testing scheme (for week 6 after Treatment 1) see Section 3.2.1.

Bladder diary measures:

Mean change from study baseline to post-treatment timepoints in the following variables:

- weekly number of UI episodes (except for week 6 after Treatment 1 which is the primary efficacy endpoint)
- total daily urinary frequency (spontaneous void and CIC)
- daily spontaneous voiding frequency
- daily CIC frequency
- total 24-hour voided volume (spontaneous void and CIC)

Statistical Analysis Plan

Version: Final v2.0

September-2018

Ipsen Protocol No. D-FR-52120-222

000000146259

Date of Issue: 21-

Covance Study ID:

- 24-hour voided volume (spontaneous void only)
- 24-hour voided volume (CIC only)
- total volume per void (spontaneous void and CIC)
- volume per void (spontaneous void only)
- volume per void (CIC only)

Proportion of subjects with:

- no episodes of UI (i.e. 100% improvement where continence is achieved)
- UI response at several levels (i.e. $\geq 30\%$ improvement, $\geq 50\%$ improvement, $\geq 75\%$ improvement)

Urodynamic filling cystometry measures:

Mean change from study baseline to week 6 after Treatment 1 in the following variables:

- MCC
- MDP during storage
- Vol@1stIDC (subjects without a post-treatment IDC will have their Vol@1stIDC imputed from their MCC)
- maximum detrusor pressure at first involuntary detrusor contraction (PdetMax@1stIDC)
- end fill pressure (EFP)
- detrusor compliance (DC)

Proportion of subjects with:

- No IDCs (i.e. urodynamic cure is achieved)

Patient-reported outcome questionnaires:

Mean change from study baseline to post-treatment timepoints in the following variables:

- I-QoL total summary score
- I-QoL Score of domain: Avoidance and limiting behaviour
- I-QoL Score of domain: Psychosocial impact
- I-QoL Score of domain: Social embarrassment
- EuroQol 5-dimension 5-level (EQ-5D-5L): Total descriptive score
- EQ-5D-5L: self-rated health (VAS)
- modified patient global impression - improvement (mPGI-I) score (to be assessed at each timepoint without comparison to baseline)

Duration of effect following the first and subsequent treatments

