6.2 Handling of Dropouts or Missing Data

6.2.1 Analysis Endpoints

6.2.1.1 Efficacy Endpoints

Refer to Section 3.1 and 3.2 for the list of primary and secondary efficacy endpoints and Section 3.2.1 for the list of secondary endpoints used in the hierarchical analysis.

Bladder diary: For data collected from the 7-day bladder diary, if there is 1 or 2 days with no data, the arithmetic means recorded (on the 5 or 6 days that do have events recorded) from the bladder diary parameters will be used for the days with no recorded bladder diary data. If there are more than 2 days of missing data, then the 7-day bladder diary data will be considered invalid.

Statistical Analysis Plan

Version: Final v2.0

September-2018

Ipsen Protocol No. D-FR-52120-222

000000146259

Date of Issue: 21-

Covance Study ID:

Primary efficacy endpoint: No imputation is planned for the primary analysis of the primary endpoint. A sensitivity analysis of the primary efficacy endpoint will be performed using multiple imputations (MI) for missing or invalid data (see Section 7.6.4.3).

Urodynamic secondary efficacy endpoints: All urodynamic data will be reviewed by independent central reviewers to determine the final values for the urodynamic parameters. Only the central reader urodynamic values will be used for analysis purposes. For the secondary efficacy endpoint of Vol@1stIDC, subjects who do not exhibit a post-treatment IDC at Week 6 after the first IMP administration will have Vol@1stIDC imputed using the recorded corrected MCC volume at Week 6.

Quality of life secondary endpoints: For I-QoL total summary score, in accordance with the I-QoL User's Manual (US English version, March 2013), if no more than three items are omitted, a normal arithmetic mean substitution will be computed for these omitted items and imputed to calculate the total summary score. If more than three items are omitted, then there will be no more imputation for those omitted items, and the total summary score will be missing. Similarly, this rule will be applied for each of the domain scores (avoiding and limiting behavior, psychosocial impact, and social embarrassment). These derived scores will be used for analysis, and the investigator recorded eCRF I-QoL total summary score, and each recorded domain score will only be listed.

The formula for the derived scale scores is as follows:

Scale Score = $\{(\text{the sum of the items} - \text{lowest possible score}) / \text{possible raw score range}\} * 100$

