For continuous endpoints analysed by mean or mean change values, inference will be done using mixed-models repeated measures, which assumes that missing outcomes are missing at random (MAR).

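### Spontaneous-only volume per void has no natural value on a day without a spontaneous void, so its exploratory Dysport-versus-placebo MMRM conditions on an outcome that treatment may change

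*SAP*

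**What the plan says.** Protocol 7.2 (Table 19) lists the measure as "Volume per void (spontaneous voiding only) on 1 day of 7-day bladder diary", with change from study baseline as the endpoint. SAP 3.2 lists it again among the diary variables. For the placebo-controlled cycle, SAP 7.6.6.1.2 states that "mean change from study baseline to Week 2, Week 6, and Week 12 will be analysed using MMRM". SAP 7.6.6 sets the comparisons as each dose against placebo at 0.05 and classes every endpoint outside the hierarchy as exploratory.

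On missing values, SAP 6.2.1.1 gives a diary rule: "if there is 1 or 2 days with no data, the arithmetic means recorded" on the remaining days are used. It also gives a rule for a urodynamic measure that can fail to exist: subjects with no involuntary contraction after treatment "will have Vol@1stIDC imputed using the recorded corrected MCC volume at Week 6". For continuous endpoints it relies on repeated-measures mixed models, "which assumes that missing outcomes are missing at random (MAR").

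On the population, Protocol 6.4.1.1 says: "All subjects in this study have significant bladder dysfunction and voiding difficulty", "requiring routine CIC usage to adequately and regularly drain urine from the bladder".

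The detailed endpoint definitions (SAP Appendix II) and diary calculations (SAP Appendix I) are not in the public text.

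**The concern.** Volume per void is a volume divided by a count. On a completed diary day with no spontaneous void, both are zero and the ratio is undefined. The 24-hour spontaneous volume and the spontaneous frequency are then simply 0. The readable diary rule covers days without data, not a completed day without a spontaneous void.

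Whether a spontaneous void occurs can plausibly change with treatment. Protocol 1.1 describes the toxin's action as weakening the injected muscle, which here is the detrusor. If fewer Dysport subjects still void spontaneously, and those who stop are the ones passing small volumes, the remaining voids look larger. The model could then report a gain in void size although no individual's voids grew. Missing at random has no clear meaning for a value that does not exist.

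At stake is the reading of one exploratory comparison per dose, at up to three visits.

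**Working it through.** **Plan figures.** The documents give no rate of spontaneous voiding, no mean volume and no SD for this measure, so there is no plan figure to reproduce. The only input they supply is 110 subjects per arm after the two placebo sequences are pooled (55 + 55). All other inputs below are assumptions.

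**Step 1: how often one day has no value.** If spontaneous voids follow a Poisson distribution with mean λ per day, P(no void) = exp(−λ).

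| λ (voids/day) | 0.25 | 0.5 | 1 | 2 | 3 |
|---|---|---|---|---|---|
| P(no value) | 78% | 61% | 37% | 14% | 5% |

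**Step 2: who contributes.** A change from baseline first needs a spontaneous void on the baseline volume day. If 30% of subjects have one, that is 0.30 × 110 = 33 per arm; if 60%, it is 66. This loss is fixed before randomisation. Now assume 20% no-void days on placebo and 60% on Dysport at Week 6:

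- 30% voiding at baseline: 33 × 0.8 ≈ 26 on placebo, 33 × 0.4 ≈ 13 on Dysport.
- 60% voiding at baseline: 66 × 0.8 ≈ 53 on placebo, 66 × 0.4 ≈ 26 on Dysport.

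This second, uneven loss arises after randomisation.

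**Step 3: effect on the planned model.** A three-visit repeated-measures model (unstructured covariance, baseline as covariate) was simulated 400 times per setting with no true effect on volume per void. Latent volume had mean 150 mL and SD √(60² + 40²) ≈ 72 mL. Placebo had 20% no-void days. The log-odds of a no-void day rose by 0, 0.5 or 1.0 for each SD of lower volume. Each range below covers 30% and 60% voiding at baseline.

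| No-void days on Dysport | Void loss unrelated to volume: bias, rejection | Low volumes lost first: bias, rejection |
|---|---|---|
| 20% (same as placebo) | −0.9 to +0.5 mL, 3.5% to 5.5% | −1.2 to +0.4 mL, 4.0% to 6.2% |
| 40% | −0.1 to +0.4 mL, 3.7% to 5.0% | +2.9 to +5.7 mL, 5.0% to 9.5% |
| 60% | −0.2 to +0.2 mL, 5.8% to 9.2% | +6.9 to +11.4 mL, 6.5% to 13.0% |

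The Monte Carlo standard error is √(0.05 × 0.95/400) ≈ 1.1 points at 5% and √(0.13 × 0.87/400) ≈ 1.7 points at 13%. The 9.2% comes from the smallest setting (26 versus 13 subjects), where the bias is only 0.2 mL. Excess rejection there cannot be put down to selection, so in the small settings the bias column is the safer guide.

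**Step 4: would scoring 0 solve it?** Take baseline voiders, 60% voiding at baseline, slope 0.5 and 200 runs. Scoring 0 gives an arm difference of −24.5 mL with 40% no-void days on Dysport and −57.3 mL with 60%. The volume of an actual void is the same in both arms. A rough check that ignores selection gives (0.6 − 0.8) × 150 = −30 mL and (0.4 − 0.8) × 150 = −60 mL. The difference reflects how often subjects void, not how much.

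**Step 5: how extreme can it get?** A simpler single-visit ANCOVA used mean 120 mL, baseline SD 50 mL and follow-up = 120 + 0.6 × (baseline − 120) + N(0, 40). It gives about 0 bias and 4% to 6% rejection when the latent correlation between volume and still voiding is 0. At correlation 0.2 to 0.3, with 90% versus 70% still voiding, it gives +2 to +3 mL and 5% to 8%. Rejection near 70% appears only with 80% voiding at baseline, 90% versus 50% still voiding and correlation 0.8.

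**The case against.** The strongest reply is that the convention may already exist. SAP 3.2 refers to Appendix II for detailed definitions, and the SAP's summary of changes shows that Appendix I holds void-volume conventions. A reader might infer that the plan has no rule; the documents do not support that, because the appendices are withheld. The point survives because neither obvious rule removes the problem: missing gives selection, and 0 gives a composite (Step 4).

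Second, the stakes are low: the endpoint is exploratory and outside the hierarchy. That stands in full.

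Third, a reader might infer a large spurious benefit for Dysport. The documents do not support this: no input comes from them, the bias vanishes if void loss is unrelated to volume, and very high rejection rates need the extreme corner of a single-visit model that is not the planned one.

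Fourth, two mechanisms are easily overstated. Catheter-only subjects at baseline reduce numbers but do not unbalance the arms. Nor does the MMRM discard everyone who stops voiding, since it keeps any baseline voider with a value at Week 2, 6 or 12. Protocol 1.6 is also weak support for loss of spontaneous voiding in this trial: it links impaired voiding to infection risk in people not catheterising.

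Fifth, the planned descriptive tables already report n, and the companion measures already have their own MMRM. This is true, but n alone does not separate a missing diary from a valid day without a spontaneous void.

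**Conclusion.** The concern holds as a limited one. Among baseline voiders, the planned contrast for spontaneous-only volume per void is conditional on a post-randomisation outcome that treatment can plausibly change. Its p-value therefore does not have a clear randomised interpretation. Size and direction cannot be derived from the documents. Under the assumed inputs, the three-visit model gives about 0 bias if void loss is unrelated to volume. If low volumes are lost first and Dysport has more no-void days, it gives roughly +3 to +11 mL and 5% to 13% rejection.

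The SAP already applies the relevant caution elsewhere. It gives a rule for volume at first involuntary contraction when no contraction occurs. It also stops between-arm testing after Week 12 because later visits depend on retreatment. The primary and six hierarchical endpoints are not touched. This is a cheap improvement, not a threat to the trial's conclusions.

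**What to change.** In SAP 7.6.6.1.2:

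1. Report spontaneous-only volume per void descriptively among subjects who void, with the number contributing, and without a between-arm p-value.
2. Add, by arm, the number with at least one spontaneous void on the volume day at baseline and at Weeks 2, 6 and 12, out of those with a valid volume day.
3. Keep the planned MMRM on daily spontaneous frequency and 24-hour spontaneous volume. Confirm, by pointing to Appendix I or II if the rule is there, that a valid diary day without a spontaneous void scores 0 for both.
4. Leave total and catheter-only volume per void as planned.

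While editing, correct the section's cross-reference: it cites 7.6.4.2 (the ANCOVA) for an MMRM that is specified in 7.6.3.

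The cost is SAP wording, one table row and the loss of one exploratory p-value (per dose and visit). No data collection changes.

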7.6.6.2 Urodynamic Filling Cystometry Parameters

See Section 3.2 for list of urodynamic endpoints. The summary tables for mean values at Week 6 and the mean change from study baseline will be presented using descriptive statistics for continuous endpoint. Number and percentage of subjects with no IDC will be also summarised.

For DBPC treatment cycle, MMRM model will be used for continuous endpoints, as described in section 7.6.3. A logistic regression will be used to analyse proportion of subject with no IDC.

Statistical Analysis Plan

Version: Final v2.0

Date of Issue: 21-

September-2018

Ipsen Protocol No. D-FR-52120-222

Covance Study ID:

000000146259

Bar charts of the LS means of changes will be plotted for MCC, MDP, Vol@1stIDC. In addition, a bar chart for the proportion of subjects with no IDC at Week 6 will be plotted.

7.6.6.3 Patient Reported Outcome Questionnaires

This includes the I-QOL, EQ-5D-5L and mPGI-I endpoints (see Section 3.2).

EQ-5D-5L comprises of the descriptive system for 5 dimensions: mobility, self-care, usual activities, pain/discomfort and anxiety/depression, where each dimension has 5 levels (1=indicating no problem, 2=indicating slight problems, 3=indicating moderate problems, 4=indicating severe problems, 5=indicating extreme problems). It also includes a self-rated health which is numbered from 0 (worst health you can imagine) to 100 (best health you can imagine):

Level	Mobility	Self-care	Usual Activities	Pain/Discomfort	Anxiety/Depression
1	I have no problems walking,	I have no problems washing or dressing myself	I have no problems doing my usual activities	I have no pain or discomfort	I am not anxious or depressed
2	I have slight problems walking,	I have slight problems washing or dressing myself	I have slight problems doing my usual activities	I have slight pain or discomfort	I am slightly anxious or depressed
3	I have moderate problems walking,	I have moderate problems washing or dressing myself	I have moderate problems doing my usual activities	I have moderate pain or discomfort	I am moderately anxious or depressed
4	I have severe problems walking,	I have severe problems washing or dressing myself	I have severe problems doing my usual activities	I have severe pain or discomfort	I am severely anxious or depressed
5	I am unable to walk	I am unable to wash or dress myself	I am unable to do my usual activities	I have extreme pain or discomfort	I am extremely anxious or depressed

The EQ-5D-5L descriptive system will be added numerically e.g. mobility=2, self-care=3, usual activities=2, pain/discomfort=3, anxiety/depression=2 gives a state=23232 i.e. slight problems with mobility, moderate problems with washing or dressing, slight problems with doing usual

Statistical Analysis Plan

Version: Final v2.0

September-2018

Ipsen Protocol No. D-FR-52120-222

000000146259

Date of Issue: 21-

Covance Study ID:

activities, moderate pain or discomfort, and slightly anxious or depressed. Missing values will be coded as a 9. The arithmetic score for the EQ-5D-5L score will be taken as $2+3+2+3+2=12$.

For both the DBPC Cycle and by the Dysport Cycles, the summary tables for mean values in each assessment visit and the mean change from study baseline will be presented using descriptive statistics.

For the DBPC Cycle for I-QOL and EQ-5D-5L, mean change from study baseline to Week 6 and Week 12, will be analysed using MMRM, similar to the primary efficacy analysis. Mean mPGI-I score at Week 2, Week 6, Week 12 will be analysed as a response variable, using MMRM as in the supportive primary analysis, without baseline factor for mPGI-I.

The LS means of change from study baseline in DBPC cycle for I-QoL total summary score at all timepoints will be presented in a line plot by treatment groups up to Week 12.

